### **Statistical Analysis**

The probability of being free of a biliary complication and the probability of liver graft survival will be estimated by the Kaplan Meier method. Continuous variables will be analyzed using Student's t test, or Wilcoxon's rank sum test. Categorical variables will be analyzed using Chi-square test or Fisher's exact test. Multivariable proportional hazards regression will be performed to adjust potential confounders. A P value of <0.05 will be considered statistically significant.

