### **Follow-up Procedure**

The patient will be followed up per standard of care for their liver transplant.

If they were randomized to receive a stent placement, they will undergo an abdominal x-ray about 3 months after transplant. This x-ray is to see if the stent has been retained in the bile duct or if it needs to be extracted by an endoscopic procedure. This abdominal x-ray is standard of care.

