### **Outcome**

Our primary outcome of interest is biliary complications. We will compare the incidence of biliary strictures, biliary leaks, cholangitis, and stones between the group that receives biliary stents and the group that does not. We will determine the time interval between transplantation to the occurrence of a complication. We will collect data on reoperations, conversion to hepaticojjunostomies, performance of an endoscopic retrograde cholangiopancreatography (ERCP) and additional hospital days incurred as a result of the biliary complication.

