### Data Sheet

Patient age at time of transplant

Gender

BMI

Etiology of cirrhosis

Listed MELD score

Calculated MELD score based on the MELD-Na formula

Total operation time

Cold ischemia time

Warm ischemia time

Stent placed at time of biliary reconstruction

Biliary complication

Type of biliary complication

Leak

Stricture

Cholangitis

Biliary stones

Retained stent

Additional procedure for stent extraction

Cost of procedure

Complications from this additional procedure

Management of biliary complication

ERCP

Sphincterotomy

Time to first biliary complication from time of transplant

Length of hospital stay for biliary complication

Readmissions

Time to first readmission

Indication for readmission

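### The plan compares incidence of biliary complications but estimates freedom from them by Kaplan-Meier, with no horizon and no rule for death or graft loss; a competing-risk cumulative incidence at a fixed time is a cheap improvement

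*Combined protocol and SAP*

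**What the plan says.** The Aim is a comparison of the incidence of biliary complications with and without a stent. The Outcome section makes biliary complications primary and says "We will compare the incidence of biliary strictures, biliary leaks, cholangitis, and stones" between the two groups. It adds "We will determine the time interval between transplantation to the occurrence of a complication", an interval that exists only for patients who have a complication.

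The Statistical Analysis section plans the following: "The probability of being free of a biliary complication and the probability of liver graft survival will be estimated by the Kaplan Meier method". It also says "Multivariable proportional hazards regression will be performed to adjust potential confounders", and it lists chi-square or Fisher tests for categorical variables without assigning them to biliary complications. It states no horizon, no censoring rule and no treatment of death or graft loss.

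On follow-up, the plan says "The patient will be followed up per standard of care for their liver transplant", with no duration. The only dated post-transplant assessment is for patients randomized to a stent: "they will undergo an abdominal x-ray about 3 months after transplant". Its purpose is to look for a retained stent, so it does not define an analysis time.

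The Data Sheet in Appendix 1 lists "Time to first biliary complication from time of transplant" and a time to first readmission. It lists no date of last follow-up, no graft loss or retransplant, and no death.

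**The concern.** Three gaps meet at the primary outcome.

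- **No time point.** Incidence has no defined value until a horizon is stated. If it is left open, it could be settled after the data are seen.
- **No rule for death or graft loss.** A patient who dies or loses the graft without a biliary complication can no longer have one in that graft. Kaplan-Meier with these patients censored estimates the risk that would apply if death and graft loss did not occur, and its complement exceeds the proportion who actually have a complication.
- **No listed censoring time.** Patients without a complication have no listed date up to which they were observed, and graft survival has no listed event or date.

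At stake is mainly whether the reported incidence means what the Aim says it means. The comparison between arms is affected much less.

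**Working it through.** The documents give no death rate, graft-loss rate, horizon or design complication rate, so the plan has no figure of its own to reproduce here. What follows illustrates size.

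**Inputs**
- About 120 randomized (Study Design). 60 per arm is an assumption, since the allocation ratio is not stated.
- 30% complications: the Background's upper figure, given there without a time point. Using it as a 12-month rate is an assumption. 20% and 15% are further assumed values.
- Competing events of 3% to 20% by 12 months, and constant hazards: assumptions.

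**Definitions at 12 months**
- F1 = true cumulative incidence of biliary complication.
- F2 = cumulative incidence of death or graft loss before any complication.
- Total cumulative hazard H = −ln(1 − F1 − F2).
- Complication cumulative hazard H1 = H × F1/(F1 + F2).
- One minus Kaplan-Meier, with F2 events censored = 1 − exp(−H1).

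**Worked case, F1 = 30%, F2 = 10%**
H = −ln(0.60) = 0.5108; H1 = 0.5108 × 0.30/0.40 = 0.3831; 1 − exp(−0.3831) = 31.8%.

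**One minus Kaplan-Meier over the assumed range**

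| F2 | true 30% reads | true 20% reads |
|---|---|---|
| 3% | 30.5% | 20.3% |
| 5% | 30.9% | 20.6% |
| 10% | 31.8% | 21.2% |
| 15% | 32.9% | 21.8% |
| 20% | 34.0% | 22.5% |

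**Sensitivity to timing, F1 = 30%, F2 = 10%**
- All competing events after the complications: 30.0%, no bias.
- All before them: 0.30/(1 − 0.10) = 33.3%.

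**Effect on the arm comparison**
- Equal competing risks, true 30% v 15% (difference 15.0 points). With 5% in both arms: 30.87 − 15.41 = 15.46. With 10% in both: 31.83 − 15.85 = 15.97 (from unrounded values). Standard error = √(0.30×0.70/60 + 0.15×0.85/60) = 7.50 points. The shifts are 0.46/7.50 = 0.06 and 0.97/7.50 = 0.13 of a standard error.
- Unequal competing risks, true 30% v 30%. With 5% v 10%: 31.83 − 30.87 = 0.95 points (unrounded). With 5% v 15%: 32.87 − 30.87 = 2.00 points. Standard error = √(2×0.30×0.70/60) = 8.37 points. The shifts are 0.95/8.37 = 0.11 and 2.00/8.37 = 0.24 of a standard error.

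**The other open choices**
- *Event definition.* In the worked case, the same data give 30.0% as a competing-risk incidence, 31.8% as the Kaplan-Meier complement, and 30 + 10 = 40% if death and graft loss count as failures.
- *Horizon.* Assume a constant hazard giving 30% at 12 months in one arm, a hazard ratio of 0.5, and complete follow-up. The monthly hazard is −ln(0.70)/12 = 0.0297. Expected events at t months are 60 × [1 − exp(−0.0297t)] + 60 × [1 − exp(−0.0149t)], which is about 8, 15, 28 and 49 at 3, 6, 12 and 24 months.

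Horizon and event definition therefore move the reported figure more than the censoring bias does.

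**The case against.** **The plan never says that one minus Kaplan-Meier will be reported as incidence.** This stands. The data sheet records complication and type as plain items, and a natural reading is that incidence means crude proportions. The overstatement then does not arise. The bias needs both conditions: death and graft loss censored, and the complement read as incidence. Crude proportions still need a common horizon when patients enter over time.

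**Kaplan-Meier and Cox analyses do not need a single horizon.** Also correct. They can use all follow-up, and a Cox model with deaths and graft losses censored is a valid cause-specific model. The horizon is needed for a quoted incidence or a test of proportions.

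**The missing fields do not make the analyses impossible.** A reader might infer that graft survival cannot be estimated, or that event-free patients cannot be censored. The documents do not support that. The sheet is not exhaustive: the Outcome section says "We will collect data on reoperations, conversion to hepaticojjunostomies", and the Limitations section names donor age, yet none of these is on the sheet. Planning a graft-survival curve implies that status and dates will be obtained. This part is missing detail.

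**The horizon will not necessarily be chosen after the data are seen.** The documents are silent on when it will be fixed. They leave the possibility open and show no more than that.

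**Conclusion.** The concern holds as a modest, conditional point and a worthwhile improvement. The stated Kaplan-Meier estimate does not match the incidence that the Aim compares, and the plan fixes neither a time point nor the handling of death and graft loss.

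If those events are censored and the complement is read as incidence, the overstatement at a true 30% is about 0.9 points with 5% competing events and 1.8 points with 10%. This assumes 12 months and constant hazards; at 10%, timing alone could move it between 0 and 3.3 points. The between-arm shifts of 0.06 to 0.24 of a standard error rest on 60 per arm and on the rates tried, and would grow only if death or graft loss differed more between arms.

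A reader might infer that the trial's comparison is materially biased. The documents give no rates that would support this. The main gain is a correctly defined incidence at a stated time.

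**What to change.** In the Statistical Analysis section:

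- Estimate first biliary complication by Aalen-Johansen cumulative incidence, with death and graft loss or retransplant as competing events, at one prespecified common horizon (for example 12 months).
- Compare arms by the difference in cumulative incidence at that horizon with a confidence interval, or by Gray's test.
- In any chi-square or Fisher test at that horizon, count patients who die or lose the graft first, without a complication, as not having had one. Report their number by arm.
- Keep the Cox model, labelled cause-specific, with death and graft loss censored.
- Keep Kaplan-Meier for graft survival with death counted as an event. If death with a functioning graft is not counted, use cumulative incidence there too.

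In Appendix 1, add dates of last follow-up, graft loss or retransplant, and death, so that event-free patients have a censoring time.

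The cost is a few data fields, probably available from routine post-transplant records, and a few lines of text. The downside is that the final analysis waits until the last patient reaches the horizon.

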### **Limitations**

Potential confounders include the etiology of liver disease, the patient's age at the time of transplant, the donor age, gender, body mass index, MELD score, the total operation time, cold ischemia time and warm ischemia time.

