## **Secondary Aim**

To retrospectively evaluate the incidence of biliary complications after liver transplantation in non-randomized patients who undergo biliary reconstruction with or without biliary stents in the same time period.

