## **Background**

Despite tremendous advances in other areas of orthotopic liver transplantation, biliary reconstruction remains a major hurdle. Morbidity related to biliary complications has been estimated to be as high as 30%. The risk of biliary complications can be related to the type of transplant performed and the technique used for reconstruction of the bile duct. One of the main techniques of performing biliary reconstruction is a choledochocholedochostomy which can be performed over an anastomotic stent.

Although placement of biliary stents is routine practice in many liver transplant centers around the country, there is no evidence to support their use. As of now both the placement and non-placement of a stent are essentially “standard of care. What has been extensively studied in the literature is the use T-tubes. In the early years of liver transplant, T-tubes were touted as a great mechanism to prevent anastomotic biliary strictures. However, their unanimous use is no longer supported as several retrospective and prospective studies have shown that their routine use led to more biliary complications including bile leaks, cholangitis, displacement of the tube, and bile duct obstruction. Although, biliary stricture formation may have been prevented, the rate of biliary complications did not offset this benefit. This was largely due to the fact that a T-tube created an additional defect in the bile duct wall. Given these findings, in the 1990s, many transplant centers started performing biliary reconstruction without the use of T-tubes.

In our center, many of our transplant surgeons now perform the biliary anastomosis over a pediatric feeding tube which is used as a stent. The hope is that use of these internal stents will help prevent post-operative biliary strictures without the added risk of biliary complications seen with T-tubes. It is expected that the stent will migrate out on its own in the early days/weeks after a transplant. However, the practice of using stents in biliary anastomosis is not uniform and there are no established guidelines to support their indiscriminate application. We have designed a prospective randomized trial to evaluate the effect of stent placement on biliary complications and its effect on morbidity.

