## **Study Design**

A randomized prospective study will be conducted of patients at Vanderbilt University Medical Center (VUMC) who undergo liver transplantation from March 1st, 2014 until approximately 120 patients are randomized. We will simultaneously perform a review of patients at VUMC who undergo liver transplantation but cannot be randomized for logistical reasons (i.e. hepatic encephalopathy, timing of the transplant procedure, or

language barriers). Data from the two groups will be evaluated independently and comparatively. The inclusion of both groups of data is critical to avoid bias in the findings due to inadvertent selection of patients who may not have the same risk for biliary complications. All data will be de-identified and stored using a secure database, REDCap.

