## **Recruitment**

Informed consent will be sought from new patients undergoing evaluation from liver transplant during their clinic visit with the transplant surgeon. For those patients currently on the waitlist for transplant, who have already undergone evaluation, consent will be sought during their subsequent upcoming clinic visits before transplant. We will also seek out patients who are currently hospitalized and are on the liver transplant waitlist. Lastly, for those patients with no clinic visits in the near future but for whom transplant is imminent, we will reach out to them at their preferred contact number to discuss the proposed project and seek informed consent.

Due to timing of the liver transplant procedure or the ability of the patient to understand the informed consent document, some patients may not be able to provide informed consent and will not qualify for randomization. Use of a stent in these patients will be determined at the discretion of the surgeon. A retrospective review of the data for these patients will be conducted.

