## **Randomization**

Patients will be prospectively randomized to 2 groups.

- Group 1 will undergo biliary reconstruction with stent placement at the anastomosis site.
- Group 2 will undergo biliary reconstruction without stent placement.

Randomization will be performed with sealed envelopes before liver transplantation. The envelope will be opened during the operation and the randomization arm will be revealed to the surgeon immediately prior to the start of the biliary anastomoses.

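### The only list of candidate covariates for the Cox model includes total operation time, which is completed after the arm is revealed, and the surgeon, who chooses the stent outside randomisation, is neither listed nor recorded

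*Combined protocol and SAP*

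**What the plan says.** **The model.** Statistical Analysis states: "Multivariable proportional hazards regression will be performed to adjust potential confounders". It does not say which covariates, or whether the model is for the randomised patients, the non-randomised patients or both.

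**The list.** Potential confounders are listed in one place only, under Limitations: etiology of liver disease, patient age, and then "the donor age, gender, body mass index, MELD score, the total operation time, cold ischemia time and warm ischemia time". The list is introduced as open-ended and is not declared to be the model's covariate set.

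**Timing.** The Randomization section says the envelope is opened during surgery and "the randomization arm will be revealed to the surgeon immediately prior to the start of the biliary anastomoses".

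**The non-randomised cohort.** The Secondary Aim is to evaluate biliary complications "in non-randomized patients who undergo biliary reconstruction with or without biliary stents in the same time period". Study Design adds: "Data from the two groups will be evaluated independently and comparatively". Recruitment says of those who cannot consent: "Use of a stent in these patients will be determined at the discretion of the surgeon". Background says "the practice of using stents in biliary anastomosis is not uniform". Surgical Procedure gives five operating surgeons.

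**The data sheet (Appendix 1).** It has a field for total operation time. It has none for the surgeon and none for any donor characteristic.

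**The concern.** Two separate comparisons are affected, by different mechanisms.

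*Randomised comparison.* A covariate that the allocated treatment can change is not a baseline variable. Suppose operation time also reflects unmeasured surgical difficulty, and difficulty drives complications. Then comparing the arms at equal operation time compares patients of unequal difficulty. Randomisation protects the unadjusted comparison from this, and adjustment can bring it in. At stake is the adjusted hazard ratio, which readers may take as the more refined result.

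*Non-randomised comparison.* Where the surgeon chooses the exposure and surgeons differ in their habits, the surgeon is an obvious candidate confounder. If complication risk differs between surgeons in line with stent preference, the stent contrast partly measures the surgeon. No listed confounder and no data-sheet field would show this.

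**Working it through.** The plan gives no figure to reproduce here: about 120 patients (Study Design) comes with no effect size or power. The check is therefore a comparison of sections, followed by illustrations.

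**1. List against data sheet.** Nine items are listed: etiology, patient age, donor age, gender, body mass index, MELD, operation time, cold ischemia and warm ischemia. Eight have a data-sheet field. Donor age does not. The surgeon is in neither place.

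**2. Timing.** The arm is revealed, the reconstruction is done, the operation ends, and only then is total operation time known. Its last part can depend on the arm. The documents do not say when the ischemia times end relative to the reveal, so the point does not extend to them.

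**3. Randomised comparison, adjusted for operation time (true HR 1.00).** Assumptions: log HR g = 0.7 per SD of unmeasured difficulty; correlation r = 0.5 or 0.7 between operation time and difficulty; stent shift d in SD of operation time; about 34% events. As an approximation, log HR(adjusted) ≈ -g·r·d. For example, at d = 0.5 and r = 0.5, exp(-0.7 × 0.5 × 0.5) = exp(-0.175) = 0.84. Large-sample Cox simulation gives:

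| Shift d | Adjusted HR |
|---|---|
| 0 | 1.00 to 1.01 |
| +0.05 | about 0.98 to 0.99 |
| +0.15 (r = 0.5) | 0.95 |
| +0.5 | 0.85 (r = 0.5), 0.80 (r = 0.7) |
| -0.15 (r = 0.5) | 1.05 |
| -0.5 | 1.18 (r = 0.5), 1.26 to 1.27 (r = 0.7) |

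The unadjusted HR stays at 1.00 to 1.01. Halving g to 0.35 moves the 0.80 to 0.88. Adding one covariate correlated 0.7 with difficulty moves it to 0.86.

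Against sampling error: at 30% (the upper figure in Background), 120 × 0.30 = 36 events and SE(log HR) ≈ 2/√36 = 0.33. Then |ln 0.80| = 0.22 is about 0.7 SE and |ln 0.95| = 0.05 is about 0.15 SE.

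**4. Surgeon in the non-randomised cohort (true HR 1.00).** Assumptions: five surgeons of equal volume, three frequent and two rare stenters; complication risks of 20% or 30%, so hazards -ln 0.8 = 0.223 and -ln 0.7 = 0.357. Worked case at 90/10 stent use with the two rare stenters at higher risk:

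- Stented: (2.7 × 0.223 + 0.2 × 0.357)/2.9 = 0.232
- Not stented: (0.3 × 0.223 + 1.8 × 0.357)/2.1 = 0.338
- Ratio: 0.232/0.338 = 0.69

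Large-sample Cox limits over every assignment of higher risk (number of assignments in brackets):

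| Stent use | Two higher-risk surgeons | Three higher-risk surgeons |
|---|---|---|
| 90/10 | 0.69 (1), 0.94 (6), 1.29 (3) | 0.79 (3), 1.06 (6), 1.44 (1) |
| 80/20 | 0.76 (1), 0.95 (6), 1.21 (3) | 0.84 (3), 1.05 (6), 1.30 (1) |
| 70/30 | 0.83 (1), 0.97 (6), 1.13 (3) | 0.89 (3), 1.03 (6), 1.19 (1) |

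At 90/10, 12 of the 20 assignments lie within about 6% of 1.00 and 8 do not. Equal risks give 1.00.

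**5. Operation time in the non-randomised cohort.** If stents are likelier in difficult cases (assumed log-odds 0.25 or 0.5 per SD), omitting operation time gives HR 1.17 or 1.35. Including it gives 0.86 to 1.25 or 0.94 to 1.39, depending on shift and correlation. Neither choice is always better.

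**The case against.** The strongest reply is that the first point rests on two inferences: that the Limitations list is the covariate list, and that it is used in the randomised comparison. Adjusting for confounders fits the non-randomised cohort at least as well, and there operation time need not be barred. This stands, so the point is conditional. It does not remove the need for a change, because if that list is not the covariate set, the plan has none.

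The bias may also be small. Only the part of the operation after the reveal can be affected, and small shifts give HRs close to 1.00. That stands too.

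Four stronger readings are tempting, and the documents do not support them:

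- *The trial's main randomised result is biased.* Outcome and Statistical Analysis already plan an unadjusted comparison of incidence and Kaplan-Meier estimates, which this does not touch.
- *Surgeon confounds the randomised comparison.* Allocation there is by envelope, so the surgeon may be prognostic but is not a confounder in expectation.
- *Surgeon and donor age will be unavailable.* The data sheet is not exhaustive. Statistical Analysis says "the probability of liver graft survival will be estimated by the Kaplan Meier method", and Outcome promises reoperations and conversions, yet none of these has a field. The omissions are data-sheet gaps only.
- *Dropping operation time costs the randomised analysis nothing.* If it is prognostic and the stent does not shift it, dropping it loses some power.

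Finally, Surgical Procedure calls the procedures standardised and every surgeon experienced. That may narrow differences in risk between surgeons but does not rule them out, and stent use itself is left to discretion.

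**Conclusion.** The concern holds in conditional form and is worth correcting, but it does not threaten the unadjusted randomised comparison. Three textual facts are certain: operation time is on the only confounder list, it is completed after the reveal, and the surgeon is on neither the list nor the data sheet. The size of any bias is not known.

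For the adjusted randomised model, the illustrative effect runs from nothing (no shift) to HRs of about 0.80 or 1.27 at half an SD. Even that extreme is about 0.7 SE with 36 events, and it shrinks if difficulty is less prognostic or partly captured by other covariates. For the non-randomised comparison, the illustrative range is 0.69 to 1.44 at 90/10 stent use, with most assignments close to 1.00. Every input is an assumption except the sample size of about 120, the 30% upper complication rate and the number of surgeons. Donor age is a minor tidy-up.

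**What to change.** In Statistical Analysis, add for the randomised patients:

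> The unadjusted result by arm will be reported. Any adjusted model will use only a short list of variables, named in advance, whose values are fixed before the envelope is opened. Total operation time is therefore excluded from that model and reported by arm.

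The list should be short because the arm plus nine single-term items is ten terms, or 36/10 = 3.6 events per term even at 30%.

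For the non-randomised patients, add:

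> Stent use will be reported by surgeon. The stent comparison will be adjusted for or stratified by surgeon, and shown with and without total operation time as a sensitivity analysis.

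In Appendix 1, add an operating-surgeon code (1 to 5) and donor age.

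**Cost.** Two fields and a few sentences, plus:

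- *Randomised adjusted model:* a small loss of power if operation time is prognostic and not shifted by the stent. In simulations with n = 120 and an assumed HR of 0.4, power was 0.69 with it and 0.68 without at correlation 0.5, and 0.71 and 0.67 at correlation 0.7, a loss of about 1 to 4 percentage points.
- *Non-randomised comparison:* lower precision. Information kept by stratifying is the within-surgeon variance of stent use over the pooled variance: 0.21/0.2484 = 85% at 70/30, 0.16/0.2464 = 65% at 80/20 and 0.09/0.2436 = 37% at 90/10. The SE rises by factors of about 1.09, 1.24 and 1.65. The size of this cohort is not stated, so whether the remaining precision is enough cannot be judged from the plan.
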